1.1 Synopsis

Protocol Title: A Phase I, Open-Label, Multiple-Dose Study of the Effect of Evobrutinib on the Pharmacokinetics of a Combined Oral Contraceptive in Healthy Female Participants

Short Title: Effect of Evobrutinib on Pharmacokinetics of a Combined Oral Contraceptive (COC)

Rationale: Embryo-fetal toxicity studies in female mice and rabbits indicate a teratogenic potential of evobrutinib. Thus, a study to evaluate the drug-drug interaction potential of evobrutinib on COC components is required according to FDA and EMA guidance.

The intent of this study is to assess the effect of evobrutinib on the pharmacokinetics of the COC ethinyl estradiol/norethisterone in healthy female participants. **CCI**

Objectives and Endpoints:

Objectives	Endpoints	Ref. #
Primary		
To investigate the effect of multiple doses of evobrutinib on EE/NET PK in healthy participants	Plasma EE/NET: AUC _{0-∞} C _{max}	1
Secondary		
To assess the safety and tolerability of evobrutinib when administered together with EE/NET in healthy participants	Nature, occurrence, and severity of TEAEs Absolute values and changes in safety laboratory tests Single 12-lead ECGs evaluated by Investigator Vital signs assessed from time of first dose to end of study participation	2 3 4 5
To characterize the effect of evobrutinib on EE/NET PK	Plasma EE/NET: t _{max} t _{1/2} AUC _{0-t_{last}} CL/F VZ/F	6

ECG=electrocardiogram; EE/NET=ethinyl estradiol/ norethisterone; PK=pharmacokinetics; TEAE=treatment-emergent adverse event.

Overall Design: This will be a nonrandomized, open-label, single-sequence, multiple-dose Phase I study in a maximum of 20 healthy female participants.

Brief Summary:

The purpose of this study is to assess the effect of evobrutinib on the pharmacokinetics of a combined oral contraceptive in healthy female participants. Study details include:

Study Duration: up to 46 days

Treatment Duration: Days 4 to 17 (14 days treatment with evobrutinib); Days 1 and 15 (2 days treatment with COC)

[figure not shown]
Visit Frequency: Participants will be resident in the Clinical Research Unit from Day -1 to Day 18.

CCI

Study Intervention Groups and Duration: single-sequence study, up to 46 days

Involvement of Special Committee(s): No

1.2 Schema

EE/NET=ethinyl estradiol/norethisterone; PK=pharmacokinetic; S=Screening visit.

a Including Safety Follow-up on Day 18 after collection of the last PK sample.

b Twice daily evobrutinib dosing starting on Day 4 under fed conditions.

1.3 Schedule of Activities

Assessments & Procedures	Screening	Intervention Period (Days)																Safety Follow-up	Notes	
		-1	1	2	3	4	5	6	7	8	9	10	11	12	13	14	15	16	17	
Study Day	-28 to -2																		18	
Informed consent	X																			Prior to any Screening activity.
Eligibility criteria	X	X ^a																		a: For re-check of eligibility criteria on Day -1, see inclusion (Section 5.1) and exclusion criteria (Section 5.2).
Demography	X																			Demography to include, at minimum, age, sex, race, and ethnicity.
Medical history	X																			
Physical examination	X	X																X	Brief examination on Day -1 to check eligibility.	
Serum pregnancy test	X	X																X		
Viral serology, TSH and QuantiFERON® test	X																			
Clinical laboratory tests including FSH	X	X														X		X	Details in Appendix 5. FSH in postmenopausal women at Screening only.	
Drug screen, alcohol breath test, and SARS-CoV-2	X	X																		
24 hours Holter ECG	X																			At Screening: 24-hour Holter ECG of participants above 45 years of age (\pm 2 hours time window allowed).
12-lead ECG	X	X	X													X	X	X		On Days -1 and 14 (predose to COC administration on Days 1 and 15); on Days 1 and 15 at 2 hours postdose \pm 30 min; and on Day 18.

Assessments & Procedures	Screening	Intervention Period (Days)																Safety Follow-up	Notes	
		-1	1	2	3	4	5	6	7	8	9	10	11	12	13	14	15	16	17	
Study Day	-28 to -2																	18		
Vital signs	X	X	X			X										X			X	Includes height and weight (collection at Screening only). Predose and 4 and 6 hours postdose on Days 4 and 14.
CCl [REDACTED]																				
Participants resident in the CRU		<----->																		
COC oral administration			X														X		Single dose of EE/NET under fed conditions. For details on dosing see Section 6.1.	
PK samples COC			X	X	X	X											X	X	X	Days 1-4, 15-18: predose and 20 min, 40 min, 1, 1.5, 2, 3, 4, 6, 8, 12, 16, 24, 36, 48, 60 and 72 hours postdose (see Section 8.4).
Evobrutinib administration						X	X	X	X	X	X	X	X	X	X	X	X	X	Evobrutinib to be dosed in the morning and the evening approximately 12 hours apart for twice daily dosing under fed conditions (see Section 6.1).	
[REDACTED]																			CCl [REDACTED]	
AE		<----->																		
Concomitant medication review		<----->																		

AE=adverse event; COC=combined oral contraceptive; CRU=clinical research unit; ECG=electrocardiogram; EE/NET=ethinyl estradiol/ norethisterone; FSH=follicle stimulating hormone; PK=pharmacokinetic; TSH=thyroid stimulating hormone.

2**Introduction**

Evobrutinib is an oral, selective, irreversible inhibitor of BTK that is in clinical development for the treatment of autoimmune diseases, e.g., RMS. Detailed information on the chemistry, pharmacology, efficacy, and safety of evobrutinib is in the IB Version 14.0 dated 20-Oct-2021.

There is extensive clinical experience of the use of the combined oral contraceptive ethinyl estradiol (EE; 0.03 mg) and norethisterone, also referred to as norethindrone (NET; 0.5 mg). See Section 2.2 for details on EE/NET.

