2.2 Background**Evobrutinib**

Evobrutinib (also known as M2951) is an oral, selective, and irreversible inhibitor of BTK. Bruton's tyrosine kinase is a crucial intracellular kinase in the B cell antigen receptor signaling pathway. The mode of action of evobrutinib via the inhibition of BTK is expected to achieve profound B cell silencing. Thus, BTK inhibition could provide clinical benefit in the treatment of multiple autoimmune diseases including RMS.

In clinical studies with healthy participants, evobrutinib was rapidly absorbed with a t_{max} of 0.5 to 1.5 hours under fasted conditions. Evobrutinib demonstrated dose-proportional PK (i.e., C_{max} and $AUC_{0-\infty}$) over the evaluated dose range of 25 to 500 mg single dose and 25 to 200 mg once daily multiple doses. Median $t_{1/2}$ was approximately 2 hours (range 1.8 to 2.6 hours) at relevant plasma concentrations following a single oral dose of 25 to 200 mg. Accumulation of evobrutinib is minimal with daily dosing (refer to IB).

CCI

CCI

Ethinyl estradiol/norethisterone

EE and NET are 2 components of many COCs and are substrates of CYP3A4. The co-administration and potential DDIs between evobrutinib and EE/NET could result in lower or higher than desired clinical concentrations of the COC components.

The combined oral contraceptive EE/NET is well characterized ([ethinyl estradiol/norethisterone SmPC, June 2021](#)) and has been previously used in similar, published DDI studies ([Loi 1999](#), [Garg 2012](#), [Shadie 2000](#)). NET is rapidly and completely absorbed after oral administration, with peak plasma concentrations occurring between 1 and 3 hours. The elimination half-life varies from 5 to 12 hours, with a mean of approximately 8 hours. EE is rapidly and well absorbed from the gastrointestinal tract but is subject to some first-pass metabolism in the gut-wall. The elimination half-life varies from 15 to 20 hours.

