2.3.3 Overall Benefit: Risk Conclusion

Risk minimization measures routinely implemented in early phase clinical studies are considered adequate, including exclusion criteria (see Section 5.2), close biochemical and hematology laboratory monitoring (see Section 8.2.4), and observation of vital signs and ECGs (see Sections 8.2.2 and 8.2.3). Evobrutinib will be discontinued in case of events that unacceptably endanger the safety of the participant (see Section 7). Participants will be admitted to the study site for the duration of the study to allow continuous safety monitoring.

Considering the measures taken to minimize the risk to participants in this study, the potential risks identified in association with evobrutinib and EE/NET are justified in healthy participants.

3 Objectives and Endpoints

Objectives	Endpoints	Ref. #
Primary		
To investigate the effect of multiple doses of evobrutinib on EE/NET PK in healthy participants	Plasma EE/NET: AUC _{0-∞} C _{max}	1
Secondary		
To assess the safety and tolerability of evobrutinib when administered together with EE/NET in healthy participants	Nature, occurrence, and severity of TEAEs	2
	Absolute values and changes in safety laboratory tests	3
	Single 12-lead ECGs evaluated by Investigator	4
	Vital signs assessed from time of first dose to end of study participation	5
	Plasma EE/NET:	6

Objectives	Endpoints	Ref. #
To characterize the effect of evobrutinib on EE/NET PK	t_{max} $t_{1/2}$ $AUC_{0-t_{last}}$ CL/F VZ/F	

CCI

ECG=electrocardiogram; EE/NET= ethinyl estradiol/norethindrone; PK=pharmacokinetics; TEAE=treatment-emergent adverse event.

4 Study Design

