6.1 Study Intervention(s) Administration

Arm Name	Evobrutinib plus combined oral contraceptive	Evobrutinib plus combined oral contraceptive
----------	--	--

Arm Type	Experimental	Experimental
Arm Description	Evobrutinib twice daily (morning and evening, approximately 12 hours apart), Days 4 to 17; and EE/NET single dose on Days 1 and 15	Evobrutinib twice daily (morning and evening), Days 4 to 17; and EE/NET single dose on Days 1 and 15
Intervention Name	Evobrutinib	EE/NET
Type	Drug	Drug
Dose Formulation	Film-coated tablet (TF2)	Film-coated tablet
Unit Dose Strength(s)	45 mg	0.03 mg/0.5 mg
Dose Amount	45 mg	0.03 mg/0.5 mg
Frequency	Twice daily	Single dose on Days 1 and 15
Route of Administration	Oral	Oral
Use	Experimental	Experimental
IMP/NIMP	IMP: Evobrutinib	IMP: EE/NET
Supplier	Merck Healthcare KGaA	Merck Healthcare KGaA
Packaging and Labeling	Study Intervention will be provided in containers. Each container will be labeled per country requirement. Additional details of packaging and labeling of study intervention will be defined in a separate IMP Handling Manual.	Study Intervention will be provided in containers. Each container will be labeled per country requirement. Additional details of packaging and labeling of study intervention will be defined in a separate IMP Handling Manual.

Each participant will receive 45 mg evobrutinib and 0.03 mg/0.5 mg EE/NET as follows (see also Schedule of Assessments in Section 1.3):

- Day 1 – single dose EE/NET:**
0.03 mg/0.5 mg EE/NET 0.5 hours after the start of a standard moderate-fat/-calorie breakfast with fasting for 4 hours postdose.
- Day 4 through Day 14 – evobrutinib twice daily:**
Morning:
45 mg evobrutinib 0.5 hours after the start of a standard moderate-fat/-calorie breakfast.

Evening:

45 mg evobrutinib (approximately 12 hours \pm 1 hour after morning dose) 0.5 hours after the start of a standardized meal.

- **Day 15 – single dose EE/NET and evobrutinib twice daily:**

Morning:

45 mg evobrutinib and 0.03 mg/0.5 mg EE/NET 0.5 hours after the start of a standard moderate-fat/-calorie breakfast with fasting for 4 hours postdose.

Evening:

45 mg evobrutinib (approximately 12 hours \pm 1 hour after morning dose) 0.5 hours after the start of a standardized meal.

- **Day 16 and Day 17 – evobrutinib twice daily:**

Morning:

45 mg evobrutinib 0.5 hours after the start of a standard moderate-fat/-calorie breakfast.

Evening:

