8.2.2 Vital Signs

- Blood pressure and participant's position; pulse; respiratory rate; temperature and location of measurement, weight, and height (at Screening only) will be measured and recorded. Temperature will be measured in the ear.

- Blood pressure and pulse measurements will be preceded by at least 5 min of rest for the participant in a quiet setting without distractions (e.g., television, cell phones) and measured with an automated device. Manual techniques will be used only if an automated device is not available.

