8.2 Subgroup Definition and Parameterization

Not applicable.

9 General Specifications for Data Analyses

The results of this study will be reported using summary tables, figures, and data listings, as appropriate. All data will be summarized by study intervention and/or scheduled time point, as applicable.

Listings

In the individual participant data listing all individual data will be listed as measured. Repeated and unscheduled measurements will be included in the listings. All listings will be sorted by subject ID and nominal time point, if not stated otherwise.

Tables and Descriptive Statistics

All safety data will be summarized overall by nominal time point, as appropriate. All PK data will be summarized by study intervention and nominal time point. Repeated and unscheduled measurements included in the listings will not be used for statistical analyses or summaries, unless the repeated measurement was performed due to unreliable values/technical reasons, e.g., clotted samples.

Unless otherwise specified, continuous variables will be summarized using descriptive statistics, i.e. the number of participants with non-missing values (n), the number of participants with missing values (nmiss), mean, standard deviation, median, 25th percentile (Q1) and 75th percentile (Q3), minimum, and maximum. If there are no missing values the number of participants with missing values should be indicated by a 0. Mean, Median, Q1, Q3, Min, Max will have the same precision as the SDTM data (decimal places). SD will be presented with one decimal place more than the mean.

Qualitative variables will be summarized by frequency counts and percentages. Unless otherwise stated the calculation of proportions will be based on the number of participants of the analysis set of interest that received the respective study intervention for AE and PK tables and for all other evaluations the analysis set of interest [N]. Therefore, counts of missing observations will be included in the denominator and presented as a separate category.

Study day 1 for this study is defined as the start date of study intervention.

The following labels will be used for the study interventions in safety and PK tables and listings, if not stated otherwise:

COC:	0.03 mg/0.5 mg EE/NET on Day 1
Evobrutinib:	45 mg Evobrutinib twice daily on Days 4 to Day 14
COC+Evobrutinib	0.03 mg/0.5 mg EE/NET on Day 15 plus 45 mg Evobrutinib twice daily on Day 15 to Day 17

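### As the Schedule best reads, no vital signs are taken on Day 15, the only day evobrutinib and EE/NET are dosed together

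*Protocol*

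**What the plan says.** Protocol 6.1 sets the dosing days: "Evobrutinib twice daily (morning and evening, approximately 12 hours apart), Days 4 to 17; and EE/NET single dose on Days 1 and 15". The secondary safety objective (Protocol 3) is "To assess the safety and tolerability of evobrutinib when administered together with EE/NET in healthy participants", and vital signs are one of its four endpoints.

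The vital-signs row of the Schedule (Protocol 1.3) is marked at Screening and on Days -1, 1, 4 and 14, with one further late mark. Its note gives times for two days only: "Predose and 4 and 6 hours postdose on Days 4 and 14". Protocol 8.2.2 lists what is measured ("respiratory rate; temperature and location of measurement, weight, and height (at Screening only) will be measured and recorded") and names no day. For the 12-lead ECG, by contrast, the note asks for recordings "on Days 1 and 15 at 2 hours postdose".

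On analysis, Protocol 9.4.2 and SAP 15.4 both summarise vital signs by treatment and time point, and SAP 15.4 limits the summary to an on-treatment period. SAP 9 labels COC+Evobrutinib as "0.03 mg/0.5 mg EE/NET on Day 15 plus 45 mg Evobrutinib twice daily on Day 15 to Day 17". SAP 9 also says that safety data are summarised overall by nominal time point, and the opening of SAP 15 likewise refers to nominal time points.

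**The concern.** The objective is about the two products given together, and its vital-signs endpoint appears to be measured on EE/NET alone (Day 1) and evobrutinib alone (Days 4 and 14) but not on the combination. Blood pressure is relevant by the protocol's own reasoning. Section 2.3.1 names cardiovascular risk with oral contraceptives and says it rises with age, Section 5.1 admits women up to 68, and Section 2.3.3 relies on vital signs and ECGs to contain risk. If Day 15 has no reading, the report can describe blood pressure, respiratory rate and temperature on the combination only from a reading taken when little of either dose remains in plasma.

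**Working it through.** **1. Overlap of dosing.** Evobrutinib is given on Days 4 to 17 and EE/NET on Days 1 and 15. The only shared day is Day 15, when both are given in the morning.

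**2. The note.** It is running text, so lost table cells cannot affect it. It names Day 14 and not Day 15. It is not a full list of days, however: Day 1 has a vital-signs mark and no time in the note.

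**3. The row, up to Day 15.** Counting cells from the left, the Day 15 cell is blank. To test whether the columns are aligned there, I used rows with isolated marks whose days are fixed elsewhere:
- EE/NET dosing: marks under Days 1 and 15, as Section 6.1 requires.
- 12-lead ECG: marks under Days 14 and 15, as its note requires.

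Both agree. Two other rows cannot serve as tests. The evobrutinib row (13 marks for 14 dosing days) and the EE/NET sampling row (three late marks for Days 15 to 18) have unbroken runs of marks there, so they would show a mark under Day 15 whichever cell was lost.

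**4. The row, after Day 15.** Here the table is damaged. The ECG mark that its note places on Day 18 sits under Day 16, so late marks have moved left. A full row has 1 label + Screening + Day -1 + 18 days + 1 note = 22 cells, and the vital-signs row has 21. Its last mark sits literally under Day 17. Restoring one lost cell puts it on Day 18, which fits the follow-up described in Protocol 1.2 ("Including Safety Follow-up on Day 18 after collection of the last PK sample"). On that reading three cells (Days 15, 16 and 17) should separate the Day 14 mark from the last one, and only two blanks are visible. The count cannot prove that the lost cell was blank.

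**5. What each reading would describe.** The half-lives are from Protocol 2.2: EE 15 to 20 h ("The elimination half-life varies from 15 to 20 hours"), NET 5 to 12 h, evobrutinib 1.8 to 2.6 h. Fraction remaining = 2^(-t/half-life), counted from dosing and ignoring absorption. Day 18 is about 72 h after EE/NET and about 12 h after the last evobrutinib dose.

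| Reading | EE | NET | Evobrutinib |
|---|---|---|---|
| Day 15, 4 h | 83–87% | 57–79% | 21–34% |
| Day 15, 6 h | 76–81% | 44–71% | 10–20% |
| Day 17, 48 h after EE/NET | 11–19% | 0.1–6% | dosing day |
| Day 18 follow-up | 4–8% | under 2% | 1–4% |

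Examples:
- EE at 72 h: 2^(-72/15) = 3.6% and 2^(-72/20) = 8.2%.
- EE at 48 h: 2^(-48/15) = 10.9% and 2^(-48/20) = 18.9%.
- NET at 48 h: 2^(-48/5) = 0.13% and 2^(-48/12) = 6.25%.
- Evobrutinib at 12 h: 2^(-12/1.8) = 1.0% and 2^(-12/2.6) = 4.1%.

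**6. Count of sets.** Days 4 and 14 have 3 timed sets each. Day 15 has 0 on the best reading.

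**The case against.** The row and the note agree with each other, so the protocol does not contradict itself. This is a descriptive pharmacokinetic study with two single doses of EE/NET. Adverse events are collected throughout, participants are resident, and the Day 15 ECG at 2 h gives heart rate. A sponsor could call the vital-signs schedule a reasonable choice. All of this stands, and it limits the weight of the point. It does not explain why the ECG covers the combination day and vital signs do not.

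The damage to the table also counts. An untimed Day 15 mark, parallel to Day 1, would not conflict with the note. A Day 17 reading would fall on an evobrutinib dosing day with some EE left. Neither would give a timed reading near the joint dose.

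A reader might infer that a Day 18 reading belongs to none of the three SAP labels, because COC+Evobrutinib stops at Day 17, and that its vital-signs cell must therefore be empty. The documents do not support this. The labels list dosing days and are not observation windows: the COC label names Day 1 only, yet its 72 h sample is drawn on Day 4. In the same way, the 72 h sample of the Day 15 profile is drawn on Day 18 and has to be reported under COC+Evobrutinib. Moreover, under the overall summary in SAP 9 there would be no treatment cell to leave empty. What remains open is narrower: the on-treatment period is undefined, and the SAP describes two different layouts for the same data.

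**Conclusion.** The point holds as a best reading, with medium confidence. Vital signs appear to have no reading on the one day both products are dosed, against three timed sets on each of Days 4 and 14. The likely next reading, on Day 18, comes when about 4 to 8% of EE, under 2% of NET and 1 to 4% of the last evobrutinib dose remain.

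This rests on the note being complete as to timed days and on the last mark being Day 18. The percentages assume simple decay in plasma. Evobrutinib binds its target irreversibly, so its effect may outlast its plasma level, and the figures do not show that Day 18 is uninformative. It would go too far to say that Day 15 has no safety coverage or that a Day 15 mark is certainly absent. The primary analysis is untouched. This is an inexpensive improvement to a secondary endpoint.

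**What to change.** 1. **Protocol 1.3.** Add Day 15 to the vital-signs row and note at the times already used on Day 14: predose, 4 h and 6 h. If the source table does carry a Day 15 mark, give it those times. Comparing Day 15 with Day 14 within participants would show the effect of adding EE/NET to evobrutinib, but not the reverse.
2. **SAP 15.4.** Define the on-treatment period, and state whether the last (Day 18) reading counts as COC+Evobrutinib or as follow-up. SAP 15.1 and 15.5 use the same undefined term, so one definition would serve all three.
3. **SAP 9, 15 and 15.4.** Reconcile the overall summary by nominal time point with the summary by treatment and time point.

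The cost is a minor amendment to one Schedule row and its note, a few SAP lines, and at most 3 x 20 = 60 short, non-invasive sets in participants who are already resident. No extra blood or visit is needed.

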2.1 Study Rationale

Embryo-fetal toxicity studies in female mice and rabbits indicate a teratogenic potential of evobrutinib (see Section 2.2). Thus, a study to evaluate the DDI potential of evobrutinib on COC components is required according to FDA and EMA guidance.

The intent of this study is to assess the effect of evobrutinib on the PK of the combined oral contraceptive EE/NET in healthy female participants. CCI

2.2 Background**Evobrutinib**

Evobrutinib (also known as M2951) is an oral, selective, and irreversible inhibitor of BTK. Bruton's tyrosine kinase is a crucial intracellular kinase in the B cell antigen receptor signaling pathway. The mode of action of evobrutinib via the inhibition of BTK is expected to achieve profound B cell silencing. Thus, BTK inhibition could provide clinical benefit in the treatment of multiple autoimmune diseases including RMS.

In clinical studies with healthy participants, evobrutinib was rapidly absorbed with a t_{max} of 0.5 to 1.5 hours under fasted conditions. Evobrutinib demonstrated dose-proportional PK (i.e., C_{max} and $AUC_{0-\infty}$) over the evaluated dose range of 25 to 500 mg single dose and 25 to 200 mg once daily multiple doses. Median $t_{1/2}$ was approximately 2 hours (range 1.8 to 2.6 hours) at relevant plasma concentrations following a single oral dose of 25 to 200 mg. Accumulation of evobrutinib is minimal with daily dosing (refer to IB).

CCI

CCI

Ethinyl estradiol/norethisterone

EE and NET are 2 components of many COCs and are substrates of CYP3A4. The co-administration and potential DDIs between evobrutinib and EE/NET could result in lower or higher than desired clinical concentrations of the COC components.

The combined oral contraceptive EE/NET is well characterized ([ethinyl estradiol/norethisterone SmPC, June 2021](#)) and has been previously used in similar, published DDI studies ([Loi 1999](#), [Garg 2012](#), [Shadie 2000](#)). NET is rapidly and completely absorbed after oral administration, with peak plasma concentrations occurring between 1 and 3 hours. The elimination half-life varies from 5 to 12 hours, with a mean of approximately 8 hours. EE is rapidly and well absorbed from the gastrointestinal tract but is subject to some first-pass metabolism in the gut-wall. The elimination half-life varies from 15 to 20 hours.

